Eligibility Criteria	
Inclusion Criteria
 
 • Conjunctivitis (as defined below) within 72 hours of initial ocular symptoms. • At least 18 years of age. • Subjects capable of understanding the purpose and risks of the study, and able to give informed consent. • Conjunctivitis diagnosis defined as presence of the two cardinal signs of acute conjunctivitis- 1) bulbar conjunctival injection and 2) conjunctival discharge/exudates. • A three-point rating scale (0=absent, 1=mild, 2=moderate, 3=severe) will be employed to grade conjunctival discharge/exudates. • All patients will require a rating of 1(mild) or greater for conjunctival discharge/exudates. • Patients will require a rating of 1 (mild) for bulbar conjunctival injection.
	
Exclusion Criteria
 
 • Conjunctivitis greater than 72 hours after initial ocular symptoms • Corneal ulcer, endophthalmitis, or any other confounding infection of the eye • Patients taking topical anti-inflammatory medications on a chronic basis • Known steroid glaucoma responders • Active herpes ocular infection • Pregnant women • Known allergy to chlorhexidine
Trial Design	This is a phase II single-center, prospective, placebo-controlled, randomized study of SCH1 in the treatment of acute infectious conjunctivitis. Study drug will be evaluated against vehicle.
Primary Endpoint	Clinical cure defined as rating of 0/3 for bulbar conjunctival injection and 0/3 for conjunctival exudates/discharge or clinical success defined as an overall decrease by 3 in the sum of both grades.

Secondary	
 Patients will keep a self log of symptom score each of the 5 days of the study
Number of Subjects	
 30 (15 per treatment arm)
Target Population	
 Patients with infectious conjunctivitis defined by bulbar conjunctival injection (rated at least 1 on 3 point grading scale) and conjunctival exudates / discharge (rated at least 1 on 3 point grading scale). Patients greater than one year of age. Patients of any race or ethnic group.
Length of Study	
Enrollment period: 12 months Treatment period: 5 days Overall duration: 6 months 5 days

Study Drug	
Subjects will be randomized to one of the following treatment arms: Treatment Arm A: SCH1 Treatment Arm B: Placebo (Vehicle only)

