Assessment of Safety	
 Incidence of SPK at day 1 Incidence of SPK at Day 5 Intraocular pressure at Day 5 
VA loss of 4 or greater lines on Snellen VA Chart

Interim Analysis and Safety Monitoring	
 Safety data will be reviewed by [name], Medical Monitor and Sponsor. A summary report of the safety points will be created every 3 months, as well as the end of the study, and reported to the IRB.
Statistical Analysis	
The statistical analysis will evaluate: 1) The overall clinical success rate defined as the percentage of study participants achieving a clinical cure by Day 5 or an overall decrease in the sum of both grades by 3; 2) Microbiological cure rate defined as the percentage of study participants who demonstrate elimination of pre-treatment pathogen(s) by the Day 5 TOC exam.
 
A statistical difference in clinical cure rate will be defined where the 95% confidence limit for the difference in the two study groups (SCH1 vs. Placebo) is greater than (+/-)15%.
 
All data will be examined employing an “Intent to Treat” analysis for all patients. Mean outcome variables in the two study groups will be compared. Statistical means between both study groups will be analyzed by both parametric and non-parametric tests to allow for deviations of data from normal distributions.

Schedule of Visits and Assessments

	Screen / Visit 1	Visit 2	Visit 3
	Day 1	Day 3	Day 5
General Exams			
Informed consent	x		
Inclusion/exclusion criteria	x		
Medical history	x		
Vital signs	x		x
Physical Exam	x		
Patient comfort exam	x	x	x
AE assessment	x	x	x
Current meds	x	x	x
Ophthalmic exams			
BCVA	x		x
Visual acuity	x	x	x
Anterior segment slit lamp exam and tonometry	x	x	x
Dilated fundus exam	x		x

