5.0 Trial Design

This is a Phase II single-center, double-masked, placebo controlled, randomized study of SCH1 for the treatment of infectious conjunctivitis. Approximately 30 subjects will be enrolled, who will be randomized in a 1:1 ratio between SCH1 and placebo. Subjects will be assessed at day 1, day 3, and day 5 for efficacy and safety.

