10.0 Assessment of Safety

The safety population is defined as all subjects who received one or more doses of SCH1. Standard summary and/or analysis techniques will be used for the evaluation of AEs, vital sign measurements, clinical laboratory results and physical examinations, and these are to be detailed within the body of the report. The safety data will be presented in individual listings and summary tables where appropriate.

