10.1 Best Corrected Visual Acuity

BCVA will be measured using ETRDRS method at each visit.

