11.0 Statistical Considerations

The clinical success rate is expected 50%-75% higher in the treatment group than in the placebo group. The microbiological cure rate is expected to be 60%-80% higher in the treatment drug arm compared to the placebo arm. Based on these estimates of efficacy, statistical and clinical significance will be demonstrable with 30 patients in each group to assure an outcome analysis with a power of >80% to detect the difference between the two groups at the 95% confidence interval.

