Descriptive statistics (i.e. mean and standard deviations [SD] for normally distributed data, median with interquartile ranges [IQR] for non-normally distributed data) were calculated for all relevant measures. Percentage breakdowns will be used for categorical variables (ie: gender, age). All P-Values will be two-sided with statistical significance evaluated at the 0.05 alpha level.

All analyses were performed in SAS Version 9.4 (SAS Institute, Inc. Cary, NC).

Determination of Sample Size

The determination of sample size was derived from clinical experience, in which we expected the clinical cure rates at day 5 to be approximately 20% and 80 % in the placebo and SCH-1 groups respectively. A sample of 15 patients per group will yield 87% power to detect a difference between 20% and 80%, based on a Fisher's exact test with a 0.05 significance level.

Changes in the Conduct of the Study or Planned Analyses

There were no changes in the conduct of the study or planned analysis.

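### The only acuity safety outcome the plan defines is a count of 4-line losses, which is very insensitive to an average loss of one to two lines, although BCVA is scheduled on Day 1 and Day 5

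*Combined protocol and SAP*

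**What the plan says.** The Synopsis, under Assessment of Safety, lists SPK on Day 1, SPK on Day 5, intraocular pressure on Day 5, and "VA loss of 4 or greater lines on Snellen VA Chart". The last is the only acuity outcome with a definition. It gives neither the reference visit nor the visit at which loss is judged.

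Acuity is also measured in its own right. Section 10.1 states: "BCVA will be measured using ETRDRS method at each visit". The Schedule of Visits marks BCVA on Day 1 and Day 5, with a separate visual acuity row at all three visits. Section 7.2 lists BCVA at Visit 1 but only visual acuity at Visits 2 and 3.

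On reporting, Section 10.0 names AEs, vital signs, laboratory results and physical examinations for standard summary, then adds: "The safety data will be presented in individual listings and summary tables where appropriate". The Synopsis says that means of unnamed outcome variables will be compared between groups. The SAP promises descriptive statistics for all relevant measures and specifies a test only for clinical cure. None of these statements names acuity.

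**The concern.** A yes/no cut at 4 lines discards most of the information in a graded measurement. If the drop lowered acuity by one or two lines in many patients, few would cross the cut, and with 15 patients per arm the counts could hardly differ convincingly. The Day 1 and Day 5 BCVA values could show such a shift, but no stated outcome uses them except through this cut.

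What is at stake is how a low count is read. The product is described as a novel combination, and safety summaries go to the IRB every 3 months and at the end of the study. Zero or one 4-line loss could be taken as evidence of no effect on acuity when it is weak evidence about anything short of a large loss.

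**Working it through.** **Inputs from the documents.** 15 per arm (Synopsis and SAP); two-sided 0.05 (SAP); BCVA on Day 1 and Day 5 (Schedule of Visits).

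**Assumptions, not in the documents.** 4 lines = 20 letters (5 letters per line); change scores normal with the same SD in both arms; mean change 0 on vehicle; mean loss 5 or 10 letters on SCH1; SD 5 to 10 letters.

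**Step 1: reproduce the plan's own figure.** The documents give none for acuity. The SAP's cure calculation states: "A sample of 15 patients per group will yield 87% power to detect a difference between 20% and 80" percent, by Fisher's exact test. Enumerating every pair of counts at 15 v 15 gives 87.2%, which agrees. The same routine is used below.

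**Step 2: what the count needs.** With 0 of 15 losses on vehicle, two-sided Fisher gives p = 0.0996 for 4 of 15 on SCH1 and p = 0.042 for 5 of 15. At least five 4-line losses are therefore needed. The plan names no test for acuity; Fisher is used here only as a yardstick.

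**Step 3: formulas.**
- Chance of a 4-line loss on SCH1: p = 1 − Φ((20 − m)/s), for mean loss m and SD s. On vehicle: p₀ = 1 − Φ(20/s).
- Expected SCH1 cases = 15p; chance of none = (1 − p)^15.
- Power on the count: sum of binomial probabilities over all pairs of counts with Fisher p ≤ 0.05.
- Power on mean change: two-sample t test, 28 degrees of freedom, noncentrality m/(s√(2/15)).

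Worked example, m = 10 and s = 8: p = 1 − Φ(1.25) = 0.106; expected cases 15 × 0.106 = 1.6; chance of none (1 − 0.1056)^15 = 0.187; noncentrality 10/(8 × 0.365) = 3.42, so power is 91%.

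**Step 4: results at 15 per arm.**

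| Mean loss (letters) | SD | Expected 4-line cases of 15 | Chance of none | Power, count | Power, mean change |
|---|---|---|---|---|---|
| 5 | 5 | 0.02 | 98% | <0.1% | 75% |
| 5 | 6 | 0.09 | 91% | <0.1% | 60% |
| 5 | 7.5 | 0.34 | 71% | <0.1% | 42% |
| 5 | 10 | 1.0 | 35% | 0.2% | 26% |
| 10 | 5 | 0.34 | 71% | <0.1% | >99% |
| 10 | 7.5 | 1.4 | 24% | 0.8% | 94% |
| 10 | 8 | 1.6 | 19% | 1.5% | 91% |
| 10 | 10 | 2.4 | 7.5% | 5.5% | 75% |

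Counting rounded losses (a cut at 3.5 lines) raises the count's power to 14% in the last row, still against 75%.

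**Step 5: precision of the added summary.** The unadjusted 95% half-width is 2.048 × s × √(2/15) = 0.748s, which is 3.7 letters at SD 5 and 7.5 letters at SD 10.

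**Step 6: the other sample size.** Section 11.0 says "statistical and clinical significance will be demonstrable with 30 patients in each group". That conflict is a separate matter. With n = 30 in the same formulas, mean loss 10 and SD 10 gives 21% on the count v 97% on mean change; mean loss 5 and SD 10 gives 0.7% v 48%. The ordering does not change.

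**The case against.** The strongest case against has four parts.

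- **Reporting is not limited to the count.** BCVA is a safety assessment under Section 10.1, and the listings in Section 10.0, the comparison of means in the Synopsis and the SAP's descriptive statistics could all show smaller changes. This stands in part: the wording permits an acuity change table but does not require one. A reader might infer that a one- or two-line average loss would be reported as no acuity loss. The documents do not support that.
- **Cases may well appear.** A reader might also infer that such a loss would normally produce no or almost no 4-line cases. That holds only for a small SD. At a mean loss of 10 letters, 81% of trials show at least one case with SD 8 and 92% with SD 10; even at a mean loss of 5 letters with SD 10, 65% do. The documents give no SD that would settle it.
- **The corneal surface is watched directly.** SPK incidence is a named outcome, Section 10.2 records corneal epithelium grading at each visit, and AEs are elicited at each visit. This lessens the risk of false reassurance. It does not measure how much acuity changed.
- **No test is planned on the count.** In a 30-patient study, a count of large losses can reasonably serve as a flag for individual review. That is a sound use and a reason to keep it. The power figures therefore show how little the count can say about a difference between arms; they do not show failure of a planned analysis.

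**Conclusion.** The point holds as a modest improvement. The 4-line count is the only acuity safety outcome defined, and no text commits to summarising change in acuity or comparing it between arms. Across the assumed SDs of 5 to 10 letters, the count has at most about 5.5% power against an average loss of one to two lines. Mean change has 26% to 75% for a 5-letter loss and 75% to over 99% for a 10-letter loss. The figures rest on 15 per arm, normal changes, 20 letters for 4 lines and no mean change on vehicle.

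The conclusion concerns insensitivity and not concealment: how many 4-line cases would be seen depends on an SD that the documents do not give. Nothing here affects the primary efficacy analysis.

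**What to change.** Keep the 4-line loss as a listing or flag, stating its reference and assessment visits. Add one sentence to the safety analysis: change in BCVA letters from Visit 1 to Visit 3 in the study eye will be summarised by arm, with the between-arm difference adjusted for the Visit 1 value and its 95% confidence interval. Say explicitly that both arms enter, because Section 10.0 defines the safety population by receipt of SCH1, and that the study eye is the one from Section 4.3, which is written for the primary analysis only.

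For this to work, reconcile the Snellen wording in the Synopsis with the ETDRS wording in Section 10.1, and the visual acuity entry for Visit 3 in Section 7.2 with the BCVA mark on Day 5 in the schedule, so that one method is used at both visits.

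The cost is that wording and one more safety table; the schedule already includes the measurements. The interval will be wide, roughly ±4 to ±7 letters before adjustment under the assumed SDs, and should be read as the range of average loss still compatible with the data, not as a test of safety.

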18.5 Publication

The first publication or disclosure of study results shall be a publication or disclosure coordinated by the Sponsor. Thereafter, all subsequent publications will reference the original publication(s).

References

1. Mahajan VM. Acute bacterial infections of the eye: their aetiology and treatment. *Br J Ophthalmol* 1983;**67**:191– 4.
3. Rietveld RP, van Weert HC, ter Riet G, Bindels PJ. Diagnostic impact of signs and symptoms in acute infectious conjunctivitis: systematic literature search. *BMJ* 2003;**327**:789.
4. Nash, EA, et. al. Patterns of emergency department visits for disorders of the eye and ocular adnexa *Arch Ophthalmol*, 1998; **116**: 1222-1226.
5. Saitoh-Inagawa W. et. al. Ten years' surveillance of viral conjunctivitis in Sapporo, Japan. *Graefes Archive for Clinical & Experimental Ophthalmolog.*, 1999; **237**:35-8.
6. Ishii K. et al. Comparative studies on aetiology and epidemiology of viral conjunctivitis in three countries of East Asia--Japan, Taiwan and South Korea. *Int Journal of Epidemiology* 1987; **16**: 98-103.
7. Aoki, K. et. al. A twenty-one year surveillance of Adenoviral Conjunctivitis in Sapporo, Japan.*Int Ophthalmol Clinics*. 2002; **42**:49-54.
8. Heggie, AD. Incidence and etiology of conjunctivitis in Navy recruits. *Mil Med*. 1990; **155**: 1-3.
9. Shields, T, et. al. A comparison of eye problems in primary care and ophthalmology practices, *Family Medicine*. 1991; **23**: 544-6.
10. Kilchington, PR et. al. Use of polymerase chain amplification reaction for the detection of adenoviruses in ocular swab specimens. *Invest Ophthalmol Vis Sci* 1994 **35**(12):4126-34.

Statistical Analysis Plan

Statistical and Analytic Plans

Chi-Square tests of homogeneity or Fisher exact tests (depending on validity of normality assumptions) were performed to assess if the distribution of the categorical outcome of clinical cure (i.e. score of zero on both conjunctival injection and conjunctival discharge) varied by treatment with either SCH-1 or placebo.

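### The synopsis and the SAP set different success rules for clinical cure, and at 15 per arm they can give opposite verdicts on the same data

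*Combined protocol and SAP*

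**What the plan says.** **Protocol synopsis, Statistical Analysis.** The rule opens "A statistical difference in clinical cure rate will be defined where" and continues that the "95% confidence limit for the difference in the two study groups (SCH1 vs. Placebo) is greater than (+/-)15" percent. It names neither the limit (lower, upper or either) nor the interval method.

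**SAP, Statistical and Analytic Plans.** The tests are "Chi-Square tests of homogeneity or Fisher exact tests (depending on validity of normality assumptions) were performed" on the "categorical outcome of clinical cure (i.e. score of zero on both conjunctival injection and conjunctival discharge"). No cut-off for choosing between them is given. On significance: "All P-Values will be two-sided with statistical significance evaluated at the 0.05 alpha level".

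**SAP, Determination of Sample Size.** The planning assumption is "we expected the clinical cure rates at day 5 to be approximately 20% and 80 % in the placebo and SCH-1 groups respectively", with 15 per group and 87% power for Fisher's "exact test with a 0.05 significance level".

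Both rules are written for clinical cure, so they compete directly. The SAP does not mention 15%, does not say which rule governs, and reports no changes to the planned analysis. The synopsis rule has therefore not been withdrawn.

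**The concern.** A difference between arms is normally shown by excluding zero. The synopsis asks for something relative to 15 points, which on its most sensible reading (lower limit above 15 points) is a stricter hurdle than p<0.05. A trial could then succeed under the SAP and fail under the synopsis.

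Within the SAP there is a second gap. At this size uncorrected chi-square and Fisher can fall on opposite sides of 0.05, and the criterion offered for choosing between them is too vague to settle which applies. The power statement covers Fisher alone.

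With about 30 patients, one or two cures decide the result. Whoever reports the trial would have to pick the rule, the limit, the interval and the test, and the documents do not make that choice in advance.

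**Working it through.** **Inputs.** 15 per arm, cure rates 20% (placebo) and 80% (SCH-1), two-sided 0.05: SAP. Margin of 15 points: synopsis. The interval method is not given, so Wald and Newcombe are both shown as assumptions. Chi-square is uncorrected unless stated.

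**1. The plan's own figure.** Power = Σ over all 16×16 tables (a, b) of Bin(a; 15, 0.80) × Bin(b; 15, 0.20), counting tables with two-sided Fisher p ≤ 0.05. Result: 0.8723. The stated 87% reproduces.

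**2. Synopsis rule against the SAP: 7/15 vs 1/15.**
- Difference: 0.4667 − 0.0667 = 0.400.
- Fisher p = 0.035; chi-square p = 0.013. Positive under the SAP by either test.
- Wald lower limit: 0.400 − 1.96 × √(0.4667×0.5333/15 + 0.0667×0.9333/15) = 0.400 − 1.96 × 0.1440 = 0.118.
- Newcombe lower limit, from Wilson limits 0.248 to 0.699 (7/15) and 0.012 to 0.298 (1/15): 0.400 − √[(0.4667−0.2481)² + (0.2982−0.0667)²] = 0.400 − 0.318 = 0.082.
- Both are below 0.15, so the result is negative under a lower-limit rule with either interval.

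**3. Chi-square against Fisher: 9/15 vs 3/15.**
- Chi-square = 30 × (9×12 − 6×3)² / (15×15×12×18) = 243,000 / 48,600 = 5.0, p = 0.025.
- Fisher p = 0.060.
- Smallest expected count = 12/2 = 6. A customary cut-off of at least 5 (an assumption; the SAP gives none) would select chi-square, not the test that was powered.

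**4. The interval method alone can decide: 10/15 vs 3/15.** Fisher p = 0.025. The lower limit is 15.4 points by Wald (passes) and 11.2 by Newcombe (fails).

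**5. Power of each rule, 15 per arm** (60% for SCH-1 is an illustrative smaller effect, not a planning value):

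| Rule | 80% vs 20% | 60% vs 20% |
|---|---|---|
| Fisher p ≤ 0.05 | 87.2% | 44.7% |
| Chi-square p ≤ 0.05 | 94.1% | 62.7% |
| Wald lower limit > 15 points | 87.1% | 43.1% |
| Newcombe lower limit > 15 points | 76.1% | 28.0% |

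**6. How often the rules disagree:**

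| Pair | 80% vs 20% | 60% vs 20% |
|---|---|---|
| Fisher positive, Wald lower limit fails | 0.09% | 1.6% |
| Fisher positive, Newcombe lower limit fails | 11.1% | 16.8% |
| Chi-square positive, Fisher not | 6.8% | 17.9% |

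No table passes the lower-limit rule, with either interval, and fails Fisher.

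**7. The upper-limit reading.** With no true difference, the upper limit exceeds 15 points in 75% (Wald) or 83% (Newcombe) of trials at a common rate of 20%, and in 84% or 82% at 50%. That reading cannot serve as a success rule.

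**8. Type I error, maximum over common rates.** Fisher 1.8%; chi-square 5.5%; the smaller of the two p-values 5.5%; chi-square when all expected counts are at least 5 and Fisher otherwise, 4.3%.

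**The case against.** Much can be said in the plan's defence, and several stronger readings do not survive it.

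- **That the trial is underpowered for its own margin.** This holds only with a Newcombe interval. With Wald, power is 87.1%, the same as planned to the nearest percent, and Fisher and the margin rule almost never disagree at the design rates. Only four tables favouring SCH-1 are Fisher-positive and fail the Wald limit (5–0, 7–1, 14–8 and 15–10). The supportable statement is 76% to 87%, depending on an interval the plan does not name.
- **That the 15% rule would pass almost any null trial.** This needs the upper limit, or either limit, to count. Since that reading makes no sense as a success rule, the likelier inference is that the lower limit was meant. The defect is that the text does not say so.
- **That choosing the test lets the analyst pick the verdict.** An expected-count rule depends only on total cures: the smallest expected count is min(total, 30 − total)/2. It ignores the treatment difference and can be applied masked. Even taking the smaller p-value keeps type I error at or below 5.5%. With a continuity correction, 9 vs 3 gives p=0.062, in agreement with Fisher.
- **That normality is irrelevant to a 2×2 table.** Too strong: chi-square rests on a normal approximation to the binomial. The wording is loose, and the real gap is the missing cut-off.
- **That the past tense of parts of the SAP shows a choice made after the results were seen.** The tense alone does not establish that.

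What stands: two rules for one outcome, no statement of which governs, and concrete tables at the planned size on which they conflict.

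**Conclusion.** The plan is inconsistent as written. Applying both documents to the same data can yield contradictory conclusions on clinical cure, and 7/15 against 1/15 shows this whichever of the two intervals is used. How often it would matter depends on what the plan leaves open. At the design rates, Fisher and a lower-limit rule disagree in 0.09% (Wald) to 11.1% (Newcombe) of trials, and chi-square and Fisher in 6.8%. The frequencies are higher if the true effect is smaller than planned.

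The 87% power figure is correct for the test it names, and there is no material inflation of type I error. The consequence is a success criterion that is not fixed in advance.

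These figures assume 15 evaluable patients per arm, as in the synopsis and SAP. Protocol Section 11.0 gives 30 per group, a separate discrepancy. At 30 per arm and the design rates, Fisher and the lower-limit rule would still disagree in 2.0% (Wald) or 3.7% (Newcombe) of trials.

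**What to change.** 1. Remove the ±15% statement from the synopsis as a definition of statistical difference. Keep 15 points at most as a descriptive benchmark.
2. In both documents, make two-sided Fisher's exact test at 0.05 the single decision rule for clinical cure. It is the only test to which the power statement is tied, so the 87% stands unchanged.
3. Report the risk difference with one named 95% interval, for example Newcombe.
4. If the sponsor does want 15 points as a formal margin, say that it applies to the lower limit, name the interval, and restate the power for that rule (76.1% with Newcombe, 87.1% with Wald, at 20% versus 80%).

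**Cost.** Wording only; no extra patients or visits. The drawback is that Fisher alone is conservative here (maximum size 1.8%). An acceptable alternative is to keep both tests with a prespecified expected-count cut-off. With at least 5, maximum size is 4.3% and power at 20% versus 80% is 93.9%, provided the power statement is updated to match. Boschloo's test performs almost identically (4.3%, 93.9%) but is optional and not needed to resolve the conflict. If outcome data have already been examined, moving to a more powerful test would be open to challenge as post hoc, which favours Fisher.
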